In summary, this study is essential for understanding why patients in Nepal fail to adhere to life-saving medications post-ACS and what can be done to mitigate this problem, ultimately improving patient care and reducing the burden on the healthcare system.

5. Objectives

a. General objectives:

To assess the level of adherence to prescribed secondary prevention medications and identify the factors influencing adherence among patients with Acute Coronary Syndrome (ACS) in Nepal.

b. Specific objectives:

- **To assess the level of adherence to secondary prevention medications (SPMs) among patients discharged after an Acute Coronary Syndrome (ACS) event, including antiplatelets, statins, beta-blockers, and ACE inhibitors/ARBs.**
- **To explore the influence of patient demographic factors** (such as age, gender, education level, occupation, and place of residence) and clinical characteristics (type of ACS, comorbidities) on medication adherence.
- **To identify patient-reported barriers to medication adherence**, including concerns about medication side effects, pill burden, practical issues with medication administration, and difficulties in integrating medications into daily routines.
- **To evaluate the relationship between medication adherence and clinical outcomes**, such as recurrent cardiac events, rehospitalization.

6. Research questions/hypothesis

- What is the level of adherence to secondary prevention medications among Acute Coronary Syndrome (ACS) patients in Nepal, and what demographic, clinical, and patient-reported factors influence this adherence and its associated clinical outcomes?

7. Research design and Methodology

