7.4 Study site and its justification

This descriptive cross-sectional study will be conducted at Manmohan Cardiothoracic Vascular and Transplant Centre, a premier tertiary care institution in Nepal, specializing in cardiovascular care. As one of the nation's leading centres for heart disease management, it offers advanced diagnostic, therapeutic, and surgical services to patients with a wide spectrum of cardiovascular conditions, including Acute Coronary Syndrome (ACS). The centre's reputation for excellence in cardiology and its strategic location make it an ideal setting for research into adherence to secondary prevention medications after ACS.

The patient population at this centre is diverse, including individuals from both urban and rural areas of Nepal, which provides a comprehensive understanding of medication adherence patterns across various demographic and socioeconomic groups. The centre regularly follows up with ACS survivors, both through outpatient visits and during readmissions for cardiac complications. This makes it a prime location to study patients who have either come for follow-up visits or been readmitted within 12 months of their initial ACS event, including STEMI, NSTEMI, and unstable angina.

By focusing on this centre, the research will leverage the expertise of its specialized staff and access to detailed patient records, providing valuable insights into medication adherence in real-world clinical practice. These insights can then be used to inform targeted interventions to improve long-term outcomes for ACS survivors across Nepal.

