7.9 Expected time and duration of the study

The study is expected to be completed in 12 months, divided as follows:

- **Months 1-2:** Ethical approval, recruitment of research assistants
- **Months 3-8:** Data collection (patient interviews, medical record review).
- **Months 9-10:** Data entry and analysis.
- **Months 11-12:** Report writing, dissemination of results, and publication

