7.10 Tools and techniques for data collection

- Tools:

Questionnaire

The questionnaire is composed of six simple-to-complete sections.

Section 1:

- Patients provide essential contextual information about the medicines they are taking, when they are administered each day, and their understanding of why they are taking them.
- This helps clinicians compare a patient's actual medication usage with documented clinical records and uncover any medication changes since discharge.

Subsequent sections (Section 2-6):

- These sections use Likert scales instead of binary yes/no responses, which improves the quality of information gathered.
- For example, it allows the assessment of the frequency of non-adherence behaviors rather than just detecting non-adherence.

Section 2:

- Explores overall understanding and satisfaction with medicines.
- Patients respond to four statements regarding their understanding of why their medicines were prescribed and how well they think they are working, using a four-point Likert scale (strongly agree, agree, disagree, strongly disagree).

Sections 3–5:

- Assess specific modifiable barriers to adherence, using the same four-point Likert scale as section 2.
- A free-text box allows patients to specify which medicines their concerns involve.

Section 3:

- Explores three areas of anxiety about medicines (e.g., concerns about medicines causing more harm than good or feeling there are too many medicines).

Section 4:

- Examines four practical concerns associated with medicine-taking (e.g., difficulties with swallowing pills or obtaining repeat prescriptions).

Section 5:

- Assesses three issues related to fitting medicines into the patient's daily routine (e.g., forgetfulness or inconvenience).
- These issues are linked to non-adherence and can potentially be addressed in clinical practice.

Section 6:

- Focuses on adherence to each individual secondary prevention medication (SPM) over the past month.
- It uses a modified version of the SQ tool and a five-point Likert scale.
- Patients are considered non-adherent if they select any answer other than 'all of the time' for any SPM.

[figure not shown]
Technique:

- A relevant questionnaire will be developed and distributed to our research team. They will visit cardiology outpatient department (OPD) as well as in the cardiology ward in Manmohan

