 - 4. Semi-skilled worker**
 - Factory or workshop laborer, laboratory or library attendant, car cleaner

5. Unskilled worker

- Watchman, peon, domestic servant, rickshaw puller

6. Unemployed

9. **Family Monthly Income (NPR):** _____

- $\geq 97,451$
- 48,751–97,450
- 36,551–48,750
- 24,351–36,550
- 14,551–24,350
- 4,851–14,550
- $\leq 4,850$

10. **Place of Residence:**

- [] Rural
- [] Urban

11. **Distance from Healthcare Facility:** _____ (km)

Section 2: Clinical Information

1. **Type of ACS:**

- [] ST-Elevation Myocardial Infarction (STEMI)
- [] Non-ST-Elevation Myocardial Infarction (NSTEMI)
- [] Unstable Angina

2. **Date of ACS Diagnosis:** _____

3. **Treatment Received:**

- [] Percutaneous Coronary Intervention (PCI)
- [] Coronary Artery Bypass Grafting (CABG)
- [] Medical Management Only

4. **Comorbidities:**

- [] Hypertension
- [] Diabetes Mellitus
- [] Dyslipidemia
- [] Chronic Kidney Disease
- [] Stroke
- [] Peripheral Arterial Disease
- [] Others (Specify): _____

Section 3: Assessment of Adherence**MYMEDS Questionnaire****Section 1: Current Medicines**

Serial Number	Name of Medicines	Administration Time (Morning/Afternoon/Evening/Night)	Reason for Taking Medicine
1	Antiplatelets	_____	_____
2	Statins	_____	_____
3	Beta-blockers	_____	_____
4	ACE inhibitors/ARBs	_____	_____
5	Others (Loop diuretics, Nitrates, specify)	_____	_____

Section Number	Statement	Strongly agree	Agree	Disagree	Strongly disagree
Section 2: Understanding and satisfaction with medicines	a. I fully understand my heart medicines and why they were prescribed.				
	b. My heart medicines seem to be working for me.				
	c. I feel convinced of the importance of all my heart medicines.				
	d. At least occasionally, I need to alter my medicines on my own to make them work or meet my expectations.				

Section 3: Concerns about medicines	a. I worry that one or more of my medicines will do me more harm than good.				
	b. I feel concerned about being prescribed too many medicines.				
	c. I sometimes alter my medicines by cutting back or stopping taking them. (e.g. due to feeling worse, getting worried or for any other reason)				
Section 4: Practical issues that may be a barrier to adherence	a. I have difficulties or problems opening the medicine bottles or blister packs and would like a solution or an alternative.				
	b. I have difficulties or problems swallowing my medicine(s) and would like a solution or an alternative.				

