	c. I have difficulties or problems getting my repeat prescriptions and would like help ordering them from my GP or pharmacy.				
	d. I have difficulties or problems reading the label on the medicines bottle or box and would like a solution or alternative.				

Section 5: Fitting medicines into daily routine	a. I sometimes forget to take my heart medicines.				
	b. I am finding it difficult to fit one or more of my heart medicines into my daily routine.				
	c. I feel inconvenienced/bothered about sticking to all my heart medicines.				

Section 6: Adherence to Individual SPMs

For each of your prescribed medicines (SPMs), please indicate how often you have taken them as prescribed in the PAST MONTH:

Medication	All of the Time	Nearly All of the Time	Most of the Time	About Half the Time	Less than Half the Time
Aspirin					
ACE Inhibitor (e.g. Ramipril, Lisinopril,)					
Beta Blocker (e.g. Acebutalol)					
Medication 4 Statin (e.g. Simvastatin)					
ARIIA (e.g. Candesartan)					

Section 4: Clinical Outcomes

1. **Have you experienced any of the following since discharge?** (Check all that apply)
 - Recurrent chest pain
 - Rehospitalization for cardiac issues
 - Stroke
 - Heart failure symptoms
 - No major events
2. **Follow-up with healthcare provider since discharge:**
 - Yes
 - No
 - If Yes, how many visits: _____

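### Objective 4 relates adherence to recurrent cardiac events, but that outcome is undefined and has no specific, dated or record-sourced item in the proforma

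*Combined protocol and SAP*

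**What the plan says.** The fourth specific objective in Section 5b is to relate adherence to clinical outcomes "such as recurrent cardiac events, rehospitalization". The project summary (Section 2) likewise promises correlations with clinical outcomes.

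The outcomes are collected in proforma Section 4 (Annex 1), under the question "Have you experienced any of the following since discharge". The patient may tick several of five boxes: "Recurrent chest pain", "Rehospitalization for cardiac issues", stroke, heart failure symptoms, and no major events. No box has a date, a cause or a count. The only clinical date on the form is "Date of ACS Diagnosis" in proforma Section 2, which is the index event.

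Section 7.9 schedules "Data collection (patient interviews, medical record review" for months 3 to 8, and Section 7.4 cites "access to detailed patient records" as a strength of the site. Neither section says that outcomes will be taken from records or checked against them. The list of study variables in 7.8 contains no clinical outcome, and Section 8 holds only headings for what an analysis plan should cover.

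On the exposure side, Section 6 of the questionnaire, as described in 7.10, "Focuses on adherence to each individual secondary prevention medication (SPM) over the past month". Under 7.7 the index ACS may lie up to 12 months back. Under 7.3 and 7.5, patients enter through outpatient follow-up or through readmission for a cardiac complication.

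**The concern.** The objective names recurrent cardiac events and rehospitalisation as two separate outcomes, but the form has a direct item only for the second. An analyst would have to build the first from a symptom (chest pain), from the rehospitalisation item, or from some mixture chosen after the data are in.

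The rehospitalisation item has its own difficulty, because readmission is also one of the two routes into the sample. Without dates, nobody can say whether an event came before or during the month for which adherence is reported. What is at stake is whether the objective 4 result can be interpreted. The adherence level and the barrier analyses do not depend on these items.

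**Working it through.** The plan gives no figure for this point, so the check is mainly a comparison of the objective with the form.

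**1. What the form can distinguish.** Take four patients and the boxes each could tick:

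| Patient | Boxes ticked |
|---|---|
| Ward, current stay is for a second MI, with chest pain | chest pain; cardiac rehospitalisation |
| Ward, current stay is for chest pain without MI | chest pain; cardiac rehospitalisation |
| Ward, one earlier cardiac readmission plus the current stay, with chest pain | chest pain; cardiac rehospitalisation |
| Outpatient, earlier readmission for a second MI, with chest pain | chest pain; cardiac rehospitalisation |

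All four records are identical. No field gives the cause or date of a readmission, and none gives the recruitment route. The form also does not say whether a ward patient should count the current stay, so a tick from such a patient may refer to this stay, an earlier one, or both.

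**2. Timing.** Adherence covers 1 month. Outcomes cover all the time since discharge, with ACS up to 12 months earlier. Assume discharge soon after the index event:
- Patient 12 months after ACS: the adherence window is 1/12 = 8% of the period, and 12 − 1 = 11 months lie before it.
- Patient 6 months after ACS: 1/6 = 17%, and 6 − 1 = 5 months lie before it.

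With no event dates, the analyst cannot tell which side of the window an event falls on.

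**3. Direction of error.** Adherence and outcomes come from the same interview. Random recall error would tend to weaken an association. A patient who under-reports both missed doses and events would push it away from zero. A patient who takes medicines more carefully after an event would push it the other way. The documents give no basis for choosing among these.

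**4. How much objective 4 could show even with better items.** The sample size in 7.6 is built for the adherence proportion: 1.96² × 0.925 × 0.075 / 0.05² = 106.60, against 106.39 as printed, raised to 117 for non-response. The plan gives no recurrence rate, so assume 5% to 10% recurrent MI/ACS, with equal risk in adherent and non-adherent patients:
- Events among 117: 117 × 0.05 = 5.9 to 117 × 0.10 = 11.7.
- Non-adherent at the plan's 92.5% adherence: 117 × 0.075 = 8.8. Events among them: 8.8 × 0.05 = 0.4 to 8.8 × 0.10 = 0.9.
- If instead half were non-adherent: 117 × 0.5 = 58.5. Events among them: 2.9 to 5.9.

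Better ascertainment makes the outcome meaningful, but it does not make the comparison precise.

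**The case against.** The strongest reply is that the objective gives examples only and speaks of cardiac events, not of MI/ACS. Chest pain, cardiac rehospitalisation and heart failure symptoms plausibly cover part of that broad term, and the second named outcome has its own box. That stands. A reader might infer that the named outcome is not measured at all, or that nothing about it could be reported. The documents do not support this, because the term is undefined and partly covered. What remains is that it is neither defined nor specifically ascertained. Section 9 itself describes rehospitalised patients as survivors of a second cardiac event, so the authors have a discrete event in mind that the form cannot identify.

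A reader might also infer that the rehospitalisation item carries no information. At most it is constant within the ward group, and only if those patients count the current stay. In the pooled outpatient and ward sample it varies.

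Third, a reader might conclude that outcome error must dilute the association. That assumes error unrelated to adherence, which a single interview does not guarantee.

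Fourth, recall is not certain to be the only source. Researchers complete the form, record review is scheduled, and Section 10 mentions excluding patients with incomplete records. The supportable criticism is that the question is addressed to the patient and no use of records for outcomes is stated.

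Repeat revascularisation might also seem to be missing, but the plan names it as an outcome nowhere, so its absence is not a gap against the plan's own objective.

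Finally, Sections 9 and 10 already acknowledge selection, survivor and cross-sectional limits. That is fair, but acknowledging them does not supply the fields needed to see their effect.

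**Conclusion.** The point holds in limited form. Recurrent cardiac events are an outcome in objective 4 with no definition, no specific item, no date and no stated record source. As the form stands:
- a recurrent MI/ACS cannot be separated from chest pain or another cardiac readmission;
- a ward patient's qualifying stay cannot be separated from an earlier one;
- events cannot be ordered against the adherence month.

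The size is qualitative: one of four specific objectives is affected, with bias of unknown direction. The conclusion rests on reading Annex 1 as the full outcome instrument, since no other is described. The event counts above rest on an assumed 5% to 10% recurrence and serve only to show that objective 4 would remain descriptive after the fix. It is worth correcting because the missing detail cannot be recovered from a completed form.

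**What to change.** 1. In 7.8, define recurrent cardiac event and list it with rehospitalisation as the clinical outcomes.
2. In proforma Section 4, add a recurrent MI/ACS item with its date, and the reason and date of each cardiac readmission.
3. Add a field for recruitment route (outpatient or ward) that marks the current stay, so that it is not confused with an earlier readmission.
4. State that these fields come from the medical record already scheduled for review, with patient report as back-up.
5. In Section 8, report the objective 4 association by recruitment route and label it descriptive.

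The cost is a few extra fields and slightly more abstraction time. The change does not cure the selection on readmission, the cross-sectional design or the small number of events, and the report should say so.

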7.1. Research method

Quantitative Survey: The adherence to secondary prevention medications among re-hospitalized patients after cardiac complications following Acute Coronary Syndrome (ACS) will be evaluated using a structured questionnaire. This survey will assess patient demographics, socioeconomic status, and barriers to adherence such as medication cost, side effects, and treatment complexity. Administered either in person or via an online platform, the survey will collect key data on adherence patterns and influencing factors in high-risk patients. This method aims to ensure efficient data collection while maintaining confidentiality and ease of access for participants.

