ADHERENCE TO SECONDARY PREVENTION MEDICATIONS AND FACTORS INFLUENCING ADHERENCE, AFTER ACUTE CORONARY SYNDROME (ACS) IN PATIENTS ATTENDING A TERTIARY CARE CENTRE OF NEPAL: A DESCRIPTIVE CROSS SECTIONAL STUDY

2. Project summary (~250 words)

This study aims to assess adherence to secondary prevention medications among patients in Nepal following an Acute Coronary Syndrome (ACS) event and identify factors affecting adherence. ACS, a major cause of morbidity and mortality globally and in Nepal, requires effective secondary prevention to minimize recurrent cardiovascular events. However, adherence to prescribed medications remains low, especially in low- and middle-income countries like Nepal. Poor adherence can lead to increased healthcare burden, worsened patient outcomes, and higher mortality rates. To address this, the study will evaluate patients' medication adherence through the MYMEDS questionnaire, a self-reported tool, which has been positively received for its simplicity and clarity.

Conducted at the Manmohan Cardiothoracic Vascular and Transplant Centre in Nepal, the study will involve a sample of adult patients readmitted or attending follow-ups post-ACS. Convenience sampling will be used, targeting approximately 117 patients to account for non-responses. The research will gather data on patient demographics, socioeconomic factors, clinical characteristics, and self-reported adherence barriers, analyzing these with SPSS to assess correlations with clinical outcomes.

The expected 12-month project will consist of phases for ethical approvals, data collection, analysis, and report dissemination. By identifying key barriers to adherence, the study aims to inform targeted interventions that could enhance medication adherence, improve long-term cardiovascular outcomes, and reduce healthcare burdens in Nepal and other similar settings.

3. Introduction

Patients experiencing myocardial infarctions (MI) are at risk of subsequent cardiovascular events and prevention of recurrent events is a major clinical and public health priority (1).

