7.3 Study population/Sampling frame

A sample of adult patients (age ≥ 18 years) who have either come to OPD for follow-up or have been readmitted for having cardiac complications months after surviving ACS (including STEMI, NSTEMI, and unstable angina) in Manmohan Cardiothoracic Vascular and Transplant Centre, Nepal will be selected via **convenience sampling**. The total population under study is around 1000.

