7.5 Sampling method

In our research study, we will employ convenience sampling. Convenience sampling is a non-probability method where units are selected for inclusion in the sample because they are the easiest for the researcher to access. The target population consists of adult patients (age ≥ 18 years) who have either come to OPD for follow-up or have been readmitted in hospital for having cardiac complications months after surviving ACS (including STEMI, NSTEMI, and unstable angina). Rather than applying specific

stratification based on cancer type, we will approach patients who are readily available within the hospital setting. We will use the MYMEDS questionnaire. The researcher will personally ask all the questions and fill out the questionnaire for each eligible patient. To assess the socioeconomic status of participants, we will utilize the Modified Kuppuswamy's Socioeconomic Status Scale, adapted to the context of Nepal (18). Alongside demographic information such as gender, age at diagnosis, and marital status, we will collect data on education level, occupation, and family income, as per the scale's criteria(18).

Once we collect the responses, we will use MS Excel for data entry and analyze the data using SPSS version 29.

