- **Adherence Rates:** We will determine the level of adherence to secondary prevention medications among patients re-hospitalized after ACS in Nepal.
- **Factors Influencing Non-Adherence:** We will identify key factors contributing to non-adherence, such as socio-economic barriers, patient knowledge, and healthcare system challenges.
- **Targeted Interventions:** The findings will inform targeted interventions to improve medication adherence and reduce re-hospitalization rates.
- **Policy Insights:** We will provide valuable insights for healthcare policy improvements in post-ACS care, helping enhance long-term cardiac outcomes in Nepal.
- **Patient Education:** The study will highlight the need for increased patient education on the importance of medication adherence.

14. Plan for dissemination of research results

- **Writing a research report:** We plan to create a detailed research report outlining the study's objectives, methodology, results, and conclusions, with an emphasis on findings related to medication adherence following acute coronary syndrome (ACS).
- **Publishing the research report:** We intend to submit the research report for publication in a reputable peer-reviewed journal focusing on cardiology or public health to ensure it reaches a scientific audience interested in ACS management and adherence studies.
- **Sharing the research report with the research team:** We will distribute the report to all members of the research team, including collaborators and supervisors, to keep everyone informed of the outcomes and enable them to incorporate findings into their ongoing work.
- **Sharing the research report with relevant stakeholders:** We plan to disseminate the report to key stakeholders such as cardiology departments to support improvements in patient care and policy development.
- **Presenting the research findings:** We will present our findings at national and international cardiology or public health conferences, allowing us to share insights with a broader audience of healthcare professionals and researchers.

15. Plan for utilization of the research finding

- **Reviewing the research findings:** We will review the research findings thoroughly to understand the implications for patient care and the management of secondary prevention adherence following acute coronary syndrome (ACS).

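### Sections 7.1 and 13 attach the adherence result to re-hospitalized patients, but outpatients are recruited too, and neither the proforma nor 7.8 records the setting in which each patient was recruited

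*Combined protocol and SAP*

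**What the plan says.** Two places name re-hospitalized patients as the population of the result. Section 7.1 sets out to evaluate "The adherence to secondary prevention medications among re-hospitalized patients after cardiac complications". Section 13 lists as its first expected outcome the "level of adherence to secondary prevention medications among patients re-hospitalized after ACS in Nepal".

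The rest of the plan is wider:

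- Specific objective 1 (section 5) reads "To assess the level of adherence to secondary prevention medications (SPMs) among patients discharged after an Acute Coronary Syndrome (ACS) event". The research question in section 6 is equally general.
- The project summary states that "the study will involve a sample of adult patients readmitted or attending follow-ups post-ACS".
- Section 7.3 samples, by convenience, adults "who have either come to OPD for follow-up or have been readmitted for having cardiac complications months after surviving ACS". Section 7.5 repeats this, section 7.4 speaks of "patients who have either come for follow-up visits or been readmitted within 12 months of their initial ACS event", and the technique text in 7.10 sends interviewers to both the OPD and the cardiology ward.
- Eligibility in 7.7 requires ACS within 12 months. It does not require readmission.

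Section 9 says that adherence behaviour may differ significantly between OPD and re-hospitalized patients and refers to comparing rates across the two groups. Section 10 adds that results may be hard to interpret uniformly across them.

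The clinical variables in 7.8 are ACS type and comorbidities. The proforma (Annex 1) asks for patient ID, demographics, ACS type and date, treatment, comorbidities, MYMEDS and outcomes since discharge. Neither has an item for recruitment setting. Section 8 holds only the prompts of the proposal template, so no analysis by setting is specified.

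**The concern.** Two things are at stake. The first is the label: section 13 states the deliverable, and a report written to it would present the rate of a mixed sample as the rate among re-hospitalized patients.

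The second is data capture. The plan itself expects the two groups to differ, but it does not collect the one variable that would show how many patients came from each and what adherence was in each. With convenience sampling and no set split, the mix follows from where interviewers spend their time. If the groups differ, the pooled rate follows the mix, and a reader cannot see by how much.

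Objective 4 ("To evaluate the relationship between medication adherence and clinical outcomes") is also touched. Rehospitalization is one of its outcomes and is also one of the two routes into the sample.

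**Working it through.** **The plan's own figure.** Section 7.6 uses z = 1.96, p = 0.925 and d = 0.05. Cochran's formula gives 1.96² × 0.925 × 0.075 / 0.05² = 106.6, against the stated 106, and 106 × 1.1 = 116.6, stated as 117. (The substituted line as printed uses other values and does not give 106; that is a separate matter.) This is one pooled estimate, with no allocation to settings.

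**Can setting be read from what is collected?** The nearest proforma item is the tick-box in Annex 1, Section 4, for cardiac readmission since discharge.

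- Unticked: suggests an OPD patient.
- Ticked: ambiguous. The item carries no date (in the clinical section only the ACS diagnosis is dated). An outpatient with an earlier readmission also ticks it, and the form does not say whether a ward patient should count the current admission.

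The box is therefore a partial proxy. Patient ID on the proforma, together with the record review in 7.9, might recover setting, but no part of the plan says this will be done.

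**How far could the mix move the pooled rate?** The documents give no adherence rate by setting and no OPD/ward mix, so everything here is assumed. The OPD rate is set at 92.5%, which is another centre's overall figure on a different scale and serves only as a starting value. With w the OPD share:

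pooled rate = w × 92.5% + (1 − w) × ward rate

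| Assumed ward rate | OPD share 20% | OPD share 80% | Shift (points) |
|---|---|---|---|
| 92.5% | 92.5% | 92.5% | 0 |
| 90% | 90.5% | 92.0% | 1.5 |
| 85% | 86.5% | 91.0% | 4.5 |
| 80% | 82.5% | 90.0% | 7.5 |

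For the last row: 0.2 × 92.5 + 0.8 × 80 = 82.5, and 0.8 × 92.5 + 0.2 × 80 = 90.0. The shift is (0.8 − 0.2) × (OPD rate − ward rate), so it exceeds 5 points only when the settings differ by more than 5 / 0.6 = 8.3 points.

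**Precision of a by-setting description.** 95% Wilson intervals on whole counts, out of 106 responders:

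- pooled, 98/106 (92.5%): 85.8% to 96.1%
- half the sample in one setting, 49/53 (92.5%): 82.1% to 97.0%
- one fifth in one setting, 19/21 (90.5%): 71.1% to 97.3%

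**The case against.** The plan already discloses the issue: section 9 names the OPD/ward difference as selection bias and section 10 lists heterogeneity. The objectives define the population broadly, so 7.1 and 13 look like a slip of wording. This is fair, and it makes the wording the smaller part of the point. The missing item remains, because disclosure does not let a reader see the mix or the rate in each group.

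The size is hypothetical. That also stands. Of the four scenarios above only one exceeds 5 points, and it needs a change of mix from 20% to 80%.

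Three stronger readings are tempting, and the documents do not support them.

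- *Setting is lost for good.* A reader might infer that the pooled rate can never be split by setting. An unticked box points to OPD, and patient ID with the record review may recover the rest. What holds is that the form does not capture setting and no step to recover it is planned.
- *The objective 4 association is an artefact of the mix.* Assume 20% non-adherence on the ward, 7.5% in OPD, 20% of outpatients with an earlier readmission, and no link between adherence and earlier readmission among outpatients. The crude odds ratio of non-adherence, ticked versus unticked, is then 2.1 at a 20% ward share and 3.0 at 80%. The dependence on mix comes from the no-link assumption. If earlier-readmitted outpatients share the ward's 20% and the others stay at 7.5%, the ratio is (0.20/0.80) / (0.075/0.925) = 3.08 at any mix. A ward/OPD difference may itself be the association that objective 4 studies. All that remains is a reason for caution.
- *The sample is too small.* A 5-point margin in each setting would need 107 per setting, 214 in all, but the plan promises no such precision by setting.

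**Conclusion.** The point holds as a mismatch of population and a gap in data capture. Sections 7.1 and 13 name a narrower population than the one the objectives define and the recruitment sections sample. Recruitment setting, which section 9 itself treats as important, is on neither the variable list nor the form, and no step to recover it is planned.

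The mislabelling follows from the text and needs no assumption about rates. The numerical effect does rest on assumed rates and mixes: none if the settings are equal, and 7.5 points at 92.5% versus 80% when the OPD share goes from 20% to 80%. These figures show what is possible and say nothing about what is likely. The pooled estimate is not shown to be invalid. For objective 4, readmission is both an entry route and an outcome, so its association with adherence needs a cautious reading. The change should be made, because it is cheap and prevents a headline rate that readers cannot place.

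**What to change.** 1. Align 7.1 and 13 with 7.3 and the objectives, so that both name OPD follow-up and readmitted patients.
2. Add a proforma item such as *Recruited from: OPD / ward readmission* and list it in 7.8. Beside the rehospitalization box, mark whether a tick refers to the current or an earlier admission. For forms already completed, take setting from the hospital record through patient ID.
3. Report the OPD/ward mix, and adherence by setting with Wilson or exact intervals, as a description alongside the pooled rate.
4. For objective 4, tabulate adherence in three groups (ward readmission, OPD with an earlier readmission, OPD without one), as a description and association only. Comparing by rehospitalization within the ward would not work, since every ward patient is a readmission.

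The cost is two tick-boxes, two edited sentences and one or two descriptive tables. The sample size stays at 106 evaluable and 117 recruited. The downside is that by-setting intervals are wider than the pooled one, as shown above, so they should not be used as formal tests between settings.
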